 - a. For the esmolol titration protocol, each hour (the closest value of heart rate to the hour) during the esmolol infusion will be determined to be “in range” or “out of range,” with 3bpm margin for compliance (i.e., heart rate 77 to 93bpm). The initiation and cessation of esmolol will also be included as a timepoint for evaluation of compliance. Protocol compliance is considered adequate where overall compliance on hourly checks is >80%.
 - b. For STOP events, protocol compliance is considered adequate at 100%.
 - i. 30min moving average of cardiac index below threshold
 - ii. 30min moving average of norepinephrine infusion rate above threshold
 - iii. Clinician determines that shock has substantially worsened on esmolol.

- c. For VOLUME EXPANSION events, protocol compliance is considered adequate at 90%.
- 4. Amount of research coordinator time spent on different tasks

2.8.1 Anticipated primary clinical outcome for main trial (this will also be recorded for ROLLIN): Organ-failure-free days at 28 days. An organ-failure-free day is defined as a calendar day on which the patient receives none of (a) vasopressor therapy, (b) mechanical ventilation, or (c) renal replacement therapy.

2.8.2 Anticipated secondary clinical outcomes for main trial (these will also be recorded for ROLLIN):

1. All-cause hospital mortality
2. All-cause 28-day and 90-day mortality
 - a. Mortality will be ascertained through telephone followup for patients who were discharged alive before 90 days.
3. Peak serum high-sensitivity troponin
 - a. Troponin will be measured on day 0 and day 1.
4. LV global longitudinal strain at 24 hours
5. Time to transition to quiescent vascular phenotype, as defined by serum Angpt-2 level < 1ng/ml.
6. ICU-free days to day 28
 - a. Patients who die before 28 days will be assigned -1 ICU-free days, using a methodology similar to that used for organ-failure-free days.
7. Cardiogenic shock/requirement for inotropes through day 14. This is a binary variable and is met when any of the following is present
 - a. Dobutamine or milrinone infusion at any dose, lasting > 60min
 - b. $CI \leq 2$ L/min/m² lasting > 30 min on NICOM
 - c. $ScvO_2 \leq 60\%$ on any measurement
8. Development of second or third degree heart block.

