ECASSS ROLL-IN Study Drug Titration protocol

Fundamental rules for study drug titration:

The target heart rate is 85 bpm. Start study drug infusion at 20 mcg/kg/min, without bolus, if HR \geq 100 bpm. If HR >90 bpm and <100 bpm, start study drug infusion at 10 mcg/kg/min, without bolus. Increase by 20 mcg/kg/min every 20 minutes as long as HR > 90 bpm, to a maximum dose of 100 mcg/kg/min. If HR < 80 bpm and > 70 bpm, decrease infusion rate by 10 mcg/kg/min; if HR ≤ 70 bpm and > 60 bpm, decrease infusion rate by 20 mcg/kg/min. Stop study drug infusion whenever a STOP EVENT occurs. Study drug infusion is completed 3 hours after vasopressor infusions have stopped. The up-titrations can be smaller than stipulated if the clinician and/or investigator feels that a small up-titration is indicated. Up-titrations should not occur during a REASSESS VOLUME STATUS event.

Study drug should be preferentially infused centrally; where no port is available, study drug should **not be** infused into a small peripheral vein or via butterfly catheter.

STOP EVENTS:

1. If HR is ever ≤ 60 bpm, immediately stop infusion for 20 minutes, then restart at half the previous infusion rate, rounded to nearest 10 mcg/kg/min. Do not resume infusion until HR > 70 bpm.
2. If vasopressor dose increases by 0.2 mcg/kg/min norepinephrine (or equivalent) AND doubles within 60 min despite adequate volume expansion, STOP the study drug infusion. Alternatively, if the treating clinician believes that the shock is worsening significantly, STOP the study drug infusion. Do not resume without explicit approval of study physician.
3. If cardiogenic shock develops ($ScvO_2 \leq 60\%$ OR LV Ejection Fraction $\leq 25\%$ OR Cardiac Index ≤ 2.0 L/min/m²), STOP the study drug infusion. Do not resume without explicit approval of study physician.
4. If clinically apparent bronchospasm develops, STOP the study drug infusion. Do not resume.
5. If Grade 2 or Grade 3 heart block develops, immediately STOP the study drug infusion. Do not resume.

REASSESS VOLUME STATUS EVENTS:

When markers of potential preload deficit occur (urine output < 0.5 ml/kg/hr OR vasopressor dosage increase), immediately EVALUATE FOR VOLUME RESPONSIVENESS. A vasopressor dosage increase is defined as at least 0.05 mcg/kg/min absolute AND 20% relative increase in the norepinephrine (or equivalent) infusion.

Titrate vasopressors as per local practice to maintain MAP ≥ 65 mmHg. Norepinephrine is the preferred primary vasopressor.

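### Titration compliance (section 2.8, item 3a) is scored by heart rate, not against the Appendix 1 rate changes, so its >80% criterion mixes patient response with staff adherence

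*Combined protocol and SAP*

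**What the plan says.** Section 2.8 item 3a sets the compliance measure for esmolol titration: "each hour (the closest value of heart rate to the hour) during the esmolol infusion will be determined to be" inside or outside a permitted band. The band allows a small tolerance and is stated "with 3bpm margin for compliance (i.e., heart rate 77 to 93bpm"). Two further timepoints are then added: "The initiation and cessation of esmolol will also be included as a timepoint for evaluation of compliance". What is judged at those two timepoints is not stated. The criterion is "Protocol compliance is considered adequate where overall compliance on hourly checks is >80"%, without saying whether overall means pooled across patients or per patient.

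The same section sets separate standards for two kinds of event: "For STOP events, protocol compliance is considered adequate at 100"% in one case, and in the other "For VOLUME EXPANSION events, protocol compliance is considered adequate at 90"%. Neither covers ordinary titration steps.

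Appendix 1 writes the titration protocol as actions. Upward: "Increase by 20 mcg/kg/min every 20 minutes as long as HR > 90 bpm, to a maximum dose of 100 mcg/kg/min". The downward rule is "If HR < 80 bpm and > 70 bpm, decrease infusion rate by 10 mcg/kg/min", with a larger decrease at lower heart rates. Smaller increases are allowed at the clinician's or investigator's discretion, and increases are barred while volume status is being reassessed.

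Section 7.2 gives the purpose of the roll-in as confirming that compliance with the management protocols is adequate. Sections 2.2 and 3.3 also ask whether the protocols themselves are adequate.

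**The concern.** Item 3a is labelled compliance, but its hourly criterion is a physiological result. Heart rate depends on whether staff made the directed rate changes and also on how the patient responded to them. The measure can therefore err in both directions: correct conduct can be scored as non-compliance, and a missed step as compliance.

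The two causes call for different responses. If steps were missed, the main trial needs better training or workflow. If steps were taken without effect, the titration protocol itself needs review. A result at or below 80% would not tell these apart, and a result above 80% would not show that due steps were taken. At stake is what the roll-in can tell the main trial about its titration procedures.

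**Working it through.** **1. The plan's own band.** Section 2.4 gives a target of 80–90/min. With the 3 bpm margin, 80 − 3 = 77 and 90 + 3 = 93, which reproduces 77–93. Appendix 1 gives the target as 85 bpm, and 85 ± 3 would be 82–88. The band therefore rests on section 2.4, and the two target statements should be reconciled.

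**2. Item 3a and Appendix 1 side by side.**

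| Situation at the hourly check | Appendix 1 | Item 3a |
|---|---|---|
| HR above 93, already at the maximum rate | no further increase available | out of range |
| HR above 93, volume status being reassessed | no increase allowed | out of range |
| HR 91–93, below the maximum, 20 min since last step, no volume hold | increase due | in range, even if not made |
| HR 77–79 | decrease directed | in range, even if not made |
| HR 80–90 | no change directed | in range |

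Of the 17 whole-number values from 77 to 93, six (77, 78, 79, 91, 92, 93) are ones at which Appendix 1 directs a change, the upper three only when an increase is due.

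**3. Full adherence, failing score.** Following Appendix 1, the rate goes 20/40/60/80/100 mcg/kg/min and reaches the maximum at 80 min, or 10/30/50/70/90/100 and reaches it at 100 min. A patient still above 93 bpm then has no upward step left. Assume pooled scoring, equal durations and all other checks in range. With r of n infused patients never in range, the overall figure is (n − r)/n:

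- n = 10: 90% for r = 1 (passes), 80% for r = 2 (fails, because the criterion is strictly above 80%), 70% for r = 3.
- n = 6 to 9: 83.3% to 88.9% for r = 1 (passes), 66.7% to 77.8% for r = 2 (fails).
- n = 5: 4/5 = 80% for r = 1 (fails).

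Fewer than 10 may count, since enrollment is up to 10 and patients who fail the final safety check are not infused. Partial non-response acts in the same way: with r of 10 patients out of range for a fraction f of their checks, the figure is 1 − rf/10, so r = 4 and f = 0.5 gives 80%.

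**4. Infusion length.** The documents fix no duration, so 24 h and 6 h are assumptions. At hour 1 the rate is still being raised, so a reading above 93 is compatible with full adherence.

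- 24 h, hour 1 out in every patient: 23/24 = 95.8%. With 1 of 10 also never in range: 0.9 × 23/24 = 86.3%. Both pass.
- 6 h, hour 1 out in every patient: 5/6 = 83.3%, a pass. With 1 of 10 also never in range: 0.9 × 5/6 = 75%, a fail.
- 6 h, if initiation also counts as a heart-rate check and is above 93: initiation and hour 1 out gives 5/7 = 71.4%, or 6/8 = 75% if an in-range cessation check is added. Both fail with no non-responder at all.

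**5. Missed steps, passing score.** A patient who starts and stays at 91–93 bpm for 24 h begins at 10 mcg/kg/min. With no volume hold and none of the five increases made, the hourly checks score 24/24 = 100%.

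**6. What an action score must avoid.** In 24 h there are 3 × 24 = 72 twenty-minute points. If correct holds earned credit, a patient at 80–90 bpm for 20 h would collect 60/72 = 83.3% with every due change missed. A non-responder at the maximum from 80 min would collect 68 of 72 points automatically. The denominator therefore has to exclude points at which no change was due.

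**The case against.** Time in the heart-rate range is a legitimate measure of whether a titration protocol reaches its target, and protocol adequacy is a stated objective. The 3 bpm margin is a deliberate tolerance, so readings of 77–79 and 91–93 are meant to be forgiven, and counting six of 17 values says nothing about how often readings fall there. Both points stand. They support keeping the measure under a heart-rate label; they do not make it show whether a due step was taken.

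A reader might infer that nothing but heart rate is scored. The text does not support that: initiation and cessation are added as timepoints and could be judged by the action taken, since their scoring is left open.

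A reader might also infer that missed steps would go unseen. Section 5.1.5 records protocol violations, and section 6.1 provides random record checks that include protocol compliance. Either could capture a missed step, because a violation is not defined. What the documents do support is narrower: neither source feeds the >80% figure.

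Finally, there are at most 10 patients, no hypothesis test on this figure and no go/no-go rule tied to it. That limits the consequence, but compliance is a listed roll-in outcome and its adequacy is what section 7.2 says the study will confirm.

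**Conclusion.** The concern holds, and the measure should be changed. Item 3a's hourly criterion does not compare infusion rates with the Appendix 1 steps, so the >80% figure cannot separate patient response from staff adherence. This follows from the text and needs no assumption.

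How often it would change the conclusion is unknown, because response rates and infusion lengths are not given. Under the assumptions in step 3, two fully adherent non-responders among 10 are enough to miss the criterion, or one among five. Short infusions are more fragile. It would be too strong to say that a fully adherent roll-in is likely to fail, or that early out-of-range checks either always or never decide the result: at 24 h they do not, at 6 h they can.

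**What to change.** - Keep the hourly 77–93 bpm measure, labelled as heart-rate control (protocol adequacy).
- Add an adherence score from the infusion record. The denominator is only the rate changes that fell due under Appendix 1: increases due below the maximum with no volume hold, and decreases due. The numerator is those made. Count permitted smaller increases as made and report them separately.
- Leave points at the maximum, in a volume hold or at 80–90 bpm out of the denominator. Count separately any change that Appendix 1 did not direct, such as an increase during a volume hold.
- Apply the titration adequacy threshold to this score. The sponsor should confirm its value and state the time window for a due change, since Appendix 1 gives 20 minutes for increases and no interval for decreases.
- Score initiation and cessation by whether they were carried out per protocol, and report results both pooled and per patient.
- Leave items 3b and 3c as they are. No dose or clinical rule changes.

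The cost is protocol wording plus abstraction of time-matched heart rate, esmolol rate and volume-event status in at most 10 patients. As a rough guide, at an assumed mean of 24 h there are 10 × 24 × 3 = 720 twenty-minute points to look through (180 at 6 h, 2,160 at 72 h). Decreases may also fall due between these points; only due changes are scored. No patient procedures are added.

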3.0 STUDY DESCRIPTION

3.1 Background

3.1.1 Septic shock is a significant clinical and scientific problem

Septic shock, a common syndrome in which infection leads to potentially fatal disruption of organismal homeostasis, accounts for 10% of all ICU admissions and 30% of all ICU mortality. Approximately 200,000 patients die annually in the USA from septic shock. Septic shock is a state of extreme biological stress associated with rapidly evolving hemodynamic, physiologic and metabolic dysfunction, as the host attempts to reestablish homeostasis in the face of severe infection.^{1,2} Progressive cardiovascular dysfunction is often the penultimate step before death from septic shock.³

3.1.2 Sympathetic nervous system over-stimulation impairs cardiovascular function in septic shock

While immune activation and autonomic nervous system stimulation are crucial to the adaptive host response to infection, in the right setting (high pathogen virulence or infectious load, genetics of the host, non-genetic susceptibility, duration of time without anti-infective therapy) these adaptive responses become pathogenic. Sympathetic over-

stimulation can drive a positive feedback loop of cardiovascular and other organ dysfunction, the “multiple organ dysfunction syndrome” (MODS), which is the signature of septic shock. The hemodynamic changes of septic shock result from dynamic interactions between cardiovascular system homeostasis, the host immune response, and therapeutic interventions such as catecholamine infusions and intravascular volume expansion.¹ Ironically, although endogenous catecholamines—which engage the widely distributed α - and β -adrenergic receptors—are increased ~20-fold in septic shock, administration of exogenous catecholamines is a cornerstone of current management.⁴ The adrenergic over-stimulation in septic shock is of central interest because (1) cardiovascular dysfunction is central to the MODS that precedes death, (2) the usual treatment paradigm for septic shock involves further adrenergic stimulation, (3) there are safe, effective, and selective adrenergic antagonists that may be beneficial in treatment of septic shock, and (4) there are now non-invasive methods to assess cardiovascular responses to septic shock and its treatment. An integrative approach to the interplay between the sympathetic nervous system and cardiovascular dysfunction in sepsis may be crucial to improving outcomes after septic shock. This harmful interplay affects both elements of the cardiovascular system: the heart and the blood vessels.

3.1.3 Adrenergic over-stimulation harms the heart

The hyper-adrenergic state, in combination with excess cytokine production, results in a spectrum of myocardial injury often grouped under the general category of septic cardiomyopathy. Septic cardiomyopathy is remarkably common, despite a historical belief that sepsis was primarily or exclusively a hyperdynamic state.^{5,6} Abnormalities of systolic¹ and diastolic^{7,8} function are independent risk factors for death from septic shock.³ Autopsy studies of septic shock demonstrate extensive myocyte injury, contraction band necrosis, and interstitial edema in 90-100% of patients.^{9,10} The catecholamine therapy used to treat septic shock may, paradoxically, worsen septic cardiomyopathy. Indeed, the extent of myocardial necrosis has been shown to correlate with dose and duration of catecholamine therapy.⁹ Recent observational studies show that catecholamine inotrope use is associated with an increased 90-day mortality in septic shock after adjusting for disease severity and propensity to receive catecholamine inotropes.⁶ Catecholamine over-stimulation can incite a parallel syndrome called “tako tsubo” or “catecholamine” cardiomyopathy in non-septic individuals. Tako tsubo cardiomyopathy shares functional, pathological, and clinical features with septic cardiomyopathy, and is also associated with increased mortality.¹¹ Though distinct from septic cardiomyopathy, tako tsubo cardiomyopathy provides independent evidence of catecholamine cardiotoxicity.

3.1.4 Adrenergic over-stimulation harms the vasculature

The cellular basis for inflammation-induced vascular permeability is well described.¹²⁻¹⁵ Junctions between adjacent endothelial cells rapidly disassemble in response to inflammatory triggers, resulting in vascular leakage. Vascular leakage not only contributes to shock, and lung injury, but inflamed endothelium posts an array of cell surface molecules that promote leukocyte adhesion and thus end organ damage.^{12-14,16} Observational studies suggest that sympathetic over-stimulation is linked to endothelial cell damage.¹⁷⁻¹⁹ Given (A) the vasculature’s emerging importance in septic shock outcomes, (B) the paucity of knowledge regarding catecholamine action on the endothelium, and (C) multiple reports that even non-septic states of adrenergic excess induce vascular inflammation and injury,²⁰⁻²³ there is a pressing need to understand how β -blockade may ameliorate the pro-leakage, pro-inflammatory vascular phenotype of septic shock.

3.1.5 The heart and blood vessels represent an integrated system

The primary expression and determinant of mortality in septic shock is the integrated host cardiac and vascular response to infection and inflammation. Inflammatory cytokine release is associated with myocardial depression, endothelial barrier dysfunction, and vascular hyporeactivity. Together, these responses lead to the classic “distributive” physiology of septic shock, compounded by increasingly recognized myocardial dysfunction. The cardiovascular system is controlled by an ancient neural-endocrine system that regulates the integrated function of heart and vessels. Via this baroreflex system, the autonomic nervous system regulates systemic perfusion by adjusting vascular tone, compliance, cardiac contractility, and heart rate. While traditionally heart and vasculature are considered separately, in reality they are an integrated system. Microvascular dysfunction within the heart results in myocardial edema, whereas extracardiac microvascular dysfunction contributes to MODS. Thus microvascular dysfunction affects both intracardiac and extracardiac vessels, contributing to septic cardiomyopathy and MODS, playing a crucial role in the pathological positive feedback loops that characterize septic shock. Furthermore, cardiac dysfunction contributes to downstream endothelial dysfunction.

Heart rate variability, a non-invasive measure of the baroreflex measured from changes in the inter-beat interval, allows for the inspection of integrated cardiovascular function. Heart rate variability provides unique insights into severity of illness in primary cardiac disease,²⁴⁻²⁶ acute trauma²⁷ and sepsis.^{28,29} In healthy states, heart rate exhibits nonlinear patterns of complexity, including fractal self-similarity across time scales.^{30,31} A technique called detrended fluctuation analysis, which quantifies the variability in inter-beat intervals over different time scales, allows the assessment of whether fractal complexity is preserved or disrupted. Fractal complexity was strongly associated with early outcomes in septic patients in research conducted by this research team³² and was associated with sepsis in neonates, a population for which heart rate variability has been extensively evaluated.³³

3.1.6. β -adrenergic blockade may be therapeutic in septic shock

Norepinephrine, the primary adrenergic agonist maintaining vasomotor tone in septic shock, commonly increases heart rate and myocardial contractility, but excessive stimulation results in cell death followed by fibrosis and pathological remodeling, effects predominantly mediated via β -adrenergic receptors. Excess catecholamines also have a direct cardiotoxic effect through oxidative damage on the myocardial membrane.³⁴ β -blockers have long demonstrated utility in non-septic myocardial dysfunction through mechanisms, including (a) inhibition of direct cardiotoxic effects of catecholamines, (b) improvement in myocardial function by reducing heart rate and oxygen demand, (c) attenuation of neurohormonal vasoconstriction and apoptotic mechanisms, and (d) protection of the microvasculature.³⁵

While advocacy for β -blockade in sepsis has recently risen, little is understood about *in vivo* mechanisms of effect during the adrenergic storm of sepsis.³⁶⁻³⁹ A pilot randomized, unblinded trial of esmolol infusion in tachycardic patients with septic shock suggested that this β 1-blocker was associated with significantly decreased mortality, higher stroke volume, lower arterial lactate, and lower norepinephrine dosage.^{40,41} Unfortunately, the control-group hospital mortality was 81%, far higher than predicted by current severity scores, thus limiting generalizability. That trial also failed to provide important mechanistic insights. Nonetheless, the positive overall result from the Italian phase 2 trial identifies both the safety of esmolol infusions in septic shock patients with tachycardia

and suggests an urgent need to conduct a more definitive and mechanistically sophisticated clinical trial.

3.1.6.1. β -adrenergic blockade has direct cardiac effects

In the heart, β -blockade improves coronary perfusion, decreases myocardial work, and directly reduces cardiomyocyte dysfunction, especially via selective β 1-blockade. The net effects can be monitored via measurement of left ventricular (LV) strain,⁴²⁻⁴⁶ a technique our group has repeatedly validated as a more sensitive and specific marker of cardiac dysfunction in septic patients. Additionally β 1-blockade may improve myocardial performance (especially through providing more time for ejection and relaxation, as measured by the tissue Myocardial Performance Index). β -blockade has long been considered an option for improving autonomic nervous system homeostasis and restoration of heart rate variability: after myocardial infarction β -blocker improves parasympathetic tone.⁴⁷

3.1.6.2. β -adrenergic blockade has effects on the microvasculature

To prevent unopposed vascular leakage and inflammation, the endothelium possesses natural braking mechanisms. The Tie2 pathway appears to be a central actor in the braking response. Tie2 is a receptor expressed predominantly by endothelial cells, where it maintains vascular barrier function.^{48,49} Normally, Tie2 is tonically activated by Angiopoietin-1 (Angpt-1), a protein ligand secreted from nearby vascular smooth muscle cells. As our group and others have shown, activated Tie2 both maintains barrier function and defends the barrier against virtually all known triggers of permeability—indeed, in the context of experimental sepsis, Tie2 activation by Angpt-1 improves organ function and survival.⁵⁰⁻⁵⁷ During inflammatory states, the function of Tie2 is antagonized by a ligand secreted from the endothelium itself called Angpt-2. Angpt-2 unseats Angpt-1 from the receptor, deactivates signaling through Tie2, and as a result, potentiates inflammation and vascular leakage. Circulating Angiopoietin levels predict vascular injury and adverse outcomes in sepsis and other critical illness,⁵⁸ while therapeutic inhibition of Angpt-2 rescues vascular leak and mortality in experimental sepsis.⁵⁹⁻⁶¹ In sum, Tie2 appears to be a major toggle for the endothelium to switch between barrier protection and vascular leakage.⁵³⁻⁵⁷

Several lines of evidence suggest that β -blockade may improve endothelial function, especially via Tie2. A pilot study of infantile hemangioma suggested a potent regressive effect of β -blockade on these benign endothelial tumors;⁶² a follow-up controlled trial demonstrated ~15-fold improvement with β -blockade.⁶³ Crucially, these inherited hemangiomatous disorders arise from mutations in *TIE2*.^{64,65} Specific to sepsis, an uncontrolled study in humans⁴⁰ and a randomized trial in rats⁶⁶ suggested that esmolol infusion significantly improved endothelial function and in turn, overall survival.

